Patients who miss scheduled follow up injection visits will be contacted and asked to reschedule their injection visit as soon as possible. If they are able to reschedule within 2 weeks then no changes to study procedure are necessary. If they are able to reschedule within 2-4 weeks then they will be asked if they have used any opiates (including fentanyl) in the past 7 days. If they have not used opiates in the past 7 days then they will resume treatment, provided they are not endorsing any signs or symptoms of liver injury. If they endorse signs or symptoms of liver injury they will undergo screening as outlined above. If they endorse using opiates then they will not be allowed to resume treatment through the study. If a patient is unable to reschedule a missed injection appointment within one month they will not be allowed to continue in the study. If a patient is unable to resume treatment through the study then they will be provided with alternative follow up options (see transition to ongoing care).

Participant Payment:

A 20-dollar gift card incentive will be used to encourage attendance at the 6 monthly follow up visits required for XR-Naltrexone injections. Gift cards will be given at each of the six visits. The total value of gift cards available to each participant during the study period is \$120.00. Gift cards will be issued for locations that do not sell alcohol (e.g. Starbucks coffee).

Study Subjects:

The target population is patients with frequent ED visits for alcohol related complaints who may benefit from ED-initiated XR-NTX. The accessible population is all people in the San Francisco Bay Area presenting to the ED with an alcohol related complaint. The study sample will be adult

patients presenting to the UCSF ED with active hazardous or high risk alcohol use and ≥ 4 ED visits in the past 12 months for alcohol related complaints.

Inclusion Criteria:

- Age ≥ 21
- AUDIT score ≥ 8
- Frequent emergency department visits, defined as: At least 3 emergency department visits for in the past 12 months, including the index visit.

Exclusion Criteria:

- Opioid use: currently receiving opioid analgesics, self-report of opioid use in past 7 days, current physiologic opioid dependence, patients in acute opioid withdrawal, urine toxicology screen positive for opiates including fentanyl
- History of hypersensitivity to naltrexone, polylactide-co-glycolide (PLG), carboxymethylcellulose, or any other components of the diluent

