XR-Naltrexone carries a risk of drug induced hepatitis. Patients will be screened with liver function tests, questioned about medical history of liver disease, and have their medical record reviewed by the emergency medicine provider to screen for history of liver disease. Patients with cirrhosis or aminotransferase levels (AST, ALT) greater than 5x the upper limit of normal will be excluded. Participants will be questioned at subsequent XR- NTX administration visits about signs and symptoms of liver injury (upper abdominal pain, abdominal bloating, vomiting, yellowing of the skin or eyes, severe fatigue/weakness, joint and muscle pain). Answers to these questions will be reviewed weekly by the PI and clinical research fellow. If the PI and/or fellow believe the participant is exhibiting evidence of liver injury, they will arrange a follow up visit at the UCSF ED within one week. At that visit if the PI or fellow feels there is sufficient clinical concern for liver injury, then laboratory testing of liver function will be conducted during the visit. Any liver function testing that occurs as a result of the PI/fellow's concern for liver injury will be considered research specific testing and outside routine clinical care. The results of any laboratory tests done to evaluate for XR-NTX induced organ injury will be followed up by the PI or clinical research fellow. Subsequent injections of XR-NTX will not be given until the PI/clinical fellow have the results and confirmed that it is safe for the patient to continue treatment. If the liver aminotransferase concentrations rise to >5 times the upper limit of normal the study medication will be discontinued and the aminotransferases will be repeated in one week. If on repeat testing the aminotransferase elevation is again above 5 times the upper limit of normal the patient will be referred for Hepatology evaluation.

XR-Naltrexone is a deep intramuscular injection and additionally carries some risk of lowering platelet counts, typically by less than 20,000 per cubic mm. Patients with platelet counts below 100,000 per cubic mm. will be excluded in order to minimize the risk of bleeding.

As with any medication, XR-Naltrexone intramuscular injection carries a risk of allergic reactions including anaphylaxis. Patients with known allergy to naltrexone or any of the inactive ingredients of the injection will be excluded.

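### For injection visits on time or up to two weeks late, no stated rule makes that day's naltrexone dose depend on the liver-symptom answers

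*Combined protocol and SAP*

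**What the plan says.** Section III (Risks and risk minimization strategy) sets the liver monitoring after the first dose:

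- "Participants will be questioned at subsequent XR- NTX administration visits about signs and symptoms of liver injury".
- "Answers to these questions will be reviewed weekly by the PI and clinical research fellow".
- If the PI or fellow suspects liver injury, "they will arrange a follow up visit at the UCSF ED within one week". Liver tests are done at that visit if concern is sufficient.
- "Subsequent injections of XR-NTX will not be given until the PI/clinical fellow have the results" and have confirmed that continuing is safe.

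Section II (Handling of missed injection visits) adds rules by lateness:

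- Up to two weeks late: "If they are able to reschedule within 2 weeks then no changes to study procedure are necessary".
- Two to four weeks late, with no opiate use in the past week: "then they will resume treatment, provided they are not endorsing any signs or symptoms of liver injury". Otherwise, "If they endorse signs or symptoms of liver injury they will undergo screening as outlined above".
- Beyond that: "If a patient is unable to reschedule a missed injection appointment within one month they will not be allowed to continue in the study".

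Under Visit 2-3 study procedures, the injection may be given by a community addiction provider or in the UCSF ED. Section V caps study-funded doses at three per participant.

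**The concern.** The symptom questions are put at the visit where the next dose is given, but the people assigned to judge the answers may not see them for up to a week. The plan accepts elsewhere that liver symptoms should stop a dose at the visit, yet it says so only for patients who come two to four weeks late. It gives no reason for leaving out patients treated nearer to schedule.

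The stakes are modest but real. Patients can enter with aminotransferases up to five times the upper limit of normal. No routine repeat liver testing is stated after the first dose, so the symptom questions are the main stated liver monitoring. Followed as written, a patient who reports symptoms could receive another month of drug before the PI or fellow knows of the report.

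**Working it through.** The plan gives no figure to reproduce. The check sets the rules side by side, followed by short arithmetic.

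**1. Which rule governs the dose at the visit where the answers are given?**

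| Injection visit | Stated liver condition on that day's dose | Source |
|---|---|---|
| Dose 1 | Yes: enrolment liver criteria | Section II, Enrollment and Exclusion Criteria |
| Doses 2 and 3, on time | None stated; answers go to weekly review | Section III, Risks |
| Doses 2 and 3, up to 2 weeks late | None added | Section II, missed visits |
| Doses 2 and 3, 2 to 4 weeks late | Yes: no liver symptoms endorsed, otherwise screening | Section II, missed visits |

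The parts on drug supply, visits 2-3, case management and adverse events add no same-day liver check before an injection.

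**2. When can the Section III hold begin?** It waits for laboratory results. The order is answers, weekly review, ED visit, tests, hold. Taking weekly to mean at most 7 days, the longest stated interval from answer to test is 7 + 7 = 14 days. A dose given on the day of the answers comes before all of these steps. Visit 2 answers can therefore protect only dose 3. Visit 3 answers protect no study dose, because none remains.

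**3. How many doses lack a stated same-day condition?**

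- Per patient: 3 − 1 = 2.
- Among 25 retained patients: 25 × 2 = 50 at most.

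The count falls for any visit in the two-to-four-week window. It rises by an unknown amount for doses given to patients who drop out and are replaced. It uses the three doses in Section V, not the six visits in the Participant Payment text.

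**4. What would a same-day hold do to timing?** Suppose a dose is held for an ED visit at most 7 days later, with results that day (turnaround is not given):

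| Days late at visit | Days late when dosed | Position |
|---|---|---|
| 0 | 0 + 7 = 7 | inside 2 weeks |
| 7 | 7 + 7 = 14 | at the 2-week limit |
| 14 | 14 + 7 = 21 | in the 2-to-4-week window |

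Each further day for results adds one day. In the last row, if the one-month limit is taken as 28 days, 28 − 21 = 7 days remain. A community kit has 7 days at room temperature from dispensing, so a full 7-day wait leaves 7 − 7 = 0 days at most.

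**The case against.** **The hold could be read more broadly.** Section III uses the same word, subsequent, for the visits at which questions are asked and for the injections that are held, so the hold might cover the dose at the questioning visit. On the narrower reading it can protect only dose 3. This does not succeed: the hold depends on results of tests that are ordered only after the review and the ED visit.

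**Serious events bypass the weekly review.** Under Adverse Events, the case manager reports serious events to the PI immediately. This stands and narrows the point to non-serious symptom reports. That route does not mention dosing, however.

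**Contact routes and clinical judgement exist.** Patients carry PI contact details, the PI can be reached by phone for emergencies, and injectors know the drug. A careful injector may well withhold a dose. That is fair, but the phone sentence sits in a paragraph on opioid analgesia, and nothing tells the injector to call or wait.

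**Stronger readings to avoid.** A reader might infer that the protocol directs injection despite symptoms. It does not; it is silent. A reader might take 50 as patients at risk. It is only a count of scheduled doses, and the documents give no rate of symptoms, of injecting despite them, or of harm. A reader might also call the screening reference in the two-to-four-week rule undefined. It can naturally mean the enrolment laboratory screening and should stay.

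**Conclusion.** The point holds as a minor safety gap. The stated review comes too late to govern the dose at the visit where symptoms are reported, and the condition that would govern it is written only for later visits. It concerns non-serious reports at visits 2 and 3 when these are on time or up to two weeks late: 2 of up to 3 doses per patient. No harm rate can be derived, and no statistical result changes. The conclusion rests on the text as written, and on treating unstated bedside judgement as not being a protocol safeguard.

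**What to change.** In Section III (Risks and risk minimization strategy), add:

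> At injection visits on time or up to 2 weeks late (ED or community), the liver-symptom questions are asked before the injection. If any symptom is endorsed, the PI or fellow is contacted the same day and decides whether that dose is given or held for evaluation.

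Keep the weekly review as a backstop. Leave the two-to-four-week rule unchanged, including its opiate stop rule, its screening and the one-month limit. If a held dose slips beyond two weeks late, those rules apply to it.

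This is a cheap improvement, but not free:

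- **Calls:** some will be for non-specific symptoms. Severe fatigue is on the liver list, and fatigue is among the commonest adverse events.
- **Longer dose intervals:** doses received and intervals between them are feasibility outcomes in Section IV, so delays should be recorded as safety holds.
- **Withdrawal:** a hold on a dose that is already late could run into the one-month limit.
- **Drug:** a held community dose may cost one kit, against the stated aim of not wasting donated medication.

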ED trackboard to determine if any patients currently in the ED at UCSF have made at least 4 ED visits in the past 12 months to UCSF or a combination of UCSF, ZSFG, or other hospitals based on shared data in our emergency department information exchange platform. If an individual is determined to be eligible based on these criteria, the faculty or study staff will review the chart for the most recent lab results including liver function tests (AST, ALT), platelets, and urine or serum pregnancy tests and urine toxicology testing specifically the presence of opioids including fentanyl (see exclusion criteria for specific cut off values). They will also review the past medical history and allergies in the electronic medical record to determine if the patient has cirrhosis or a document allergy to naltrexone or inactive ingredients contained in naltrexone XR. When a patient is determined to meet criteria inclusion by electronic record review, a study staff member will discuss the case with the ED provider caring for the patient to confirm the patient is willing to be approached, is clinically sober, and medically stable. The ED provider will then introduce the patient to the research staff who will discuss the study with the patient. The research staff member will assess the patient's willingness to participate. If a patient expresses interest in participating the research staff member will confirm the accuracy of information obtained from the medical record review that pertains to inclusion and exclusion criteria. If no discrepancies are found the research team member describe the study in detail and will perform a capacity assessment using the University of California San Diego Brief Assessment of Capacity to Consent to Research (UBACC) if there are any concerns about the participant's capacity to consent, such as ongoing alcohol or drug intoxication or withdrawal.

Capacity Assessment:

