The UBACC is a validated 10-item questionnaire used previously in this population [16,17]. It rates the basic elements of capacity (understanding, appreciation, reasoning, and ability to express a choice) to identify subjects with questionable capacity to consent to a specified research project. Administration of the UBACC will occur after informing the patient about the study. The consenter will review each page of the informed consent document with the patient, pausing to reassess comprehension throughout the process. Then they will administer the UBACC. Once the patient's understanding is confirmed by the UBACC, the consenter will request the patient's signature and provide the patient with a copy of the signed consent document. If the consenter doubts the patient's comprehension of the study procedures the patient will not be enrolled at that time, but may be eligible in the future. Once capacity is established the patient will be asked to provide informed consent.

Consent:

Patients deemed to be eligible for enrollment after electronic record review may be approached by a member of the research team to assess willingness to participate. For patients interested in participating consent will occur only after the patient is clinically sober as judged by the treating ED provider and their capacity to consent has been established by the consenter, using the UBACC if necessary. The consenter will provide patients with information about the study, including risks and benefits of treatment with extended release naltrexone both verbally and in print. If the patient wishes to enroll in the study they will be consented by a member of the research team (research case manager, PI, research fellow) and sign the consent document.

With the exception of the research case manager, all members of the research team are practicing Emergency Medicine Physicians who frequently obtain informed consent for a variety of procedures performed while caring for patients in the emergency department and have completed required human subjects research training.

The research case manager will be trained in obtaining informed consent by completing the required training modules for UCSF human subjects researchers and be trained in the teach back method and use of the UBACC by the study PI, [name].

Enrollment:

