Patients identified as frequent ED users will undergo an alcohol use disorder screening conducted by the research case manager, PI, or research fellow using a validated screening tool, the Alcohol Use Disorder Identification Test (AUDIT) which constitutes the screening component of SBIRT. The AUDIT places patients into one of four categories: low risk, risky, harmful, and severe. Brief intervention and pharmacotherapy have previously been shown to be most effective in those with harmful or severe use disorders [12]. Patients found to have at least harmful alcohol use based on the screening will be offered enrollment (AUDIT score ≥ 8). Enrollees will have blood and urine samples collected to screen for active opiate use including fentanyl, platelet counts, pregnancy, or significant liver disease (see exclusion criteria below) if no results are available in EHR. With the exception of urine pregnancy screening these tests are done as part of the routine care of emergency department patients with alcohol use disorders who are interested in accessing treatment. The results will be used to confirm inclusion/exclusion criteria are met. Patients meeting all criteria will be enrolled into the study and will receive 380mg of extended-release naltrexone as an intramuscular injection in the ED.

Naltrexone training and administration:

Study staff will compose and send e-mail before the start of the study, with input from UCSF ED nursing leadership, to all ED RNs informing of the intent and responsibilities of the study. Subsequently, during RN sign out (twice daily at 7am and 7pm) study staff will remind ED RNs about the study protocol to ensure as much staff as possible is aware of RN involvement and responsibilities. The shift-change information session will be performed for a two week run in period to assure all RNs are oriented.

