Data collected for this study includes details about alcohol and recreational drug use as well as information about employment and housing status. These topics may be sensitive to discuss, but are part of routine medical interviewing. Information collected by the research team will be taken place in a private room and data stored securely (see data management plan).

No EDs in San Francisco administer Naltrexone, so there is no concern that a patient will receive extra doses during ED visits at locations other than UCSF. There are community sites, such as the San Francisco sobering center, SF street medicine and Health Right 360, where XR-Naltrexone is available and is administered to patients. These community sites are key stakeholders in the treatment of patients with AUD. One of the aims of this study is to establish a robust referral network for ongoing treatment of AUD once patients are discharged from the hospital/ED by mobilizing key stakeholders. We will coordinate with leadership and staff of community organizations that treat AUD throughout the study timeframe by forming a stakeholder committee that includes representatives from SF Street medicine, Health Right 360, and UCSF providers about both facilitators of and barriers to continuity of care after the initial ED visit and throughout the study. The committee will also serve as a venue for stakeholders to express any safety concerns, and will review any adverse events. The committee will meet quarterly and will record meeting proceedings and create a meeting summary.

Risk/Benefit balance:

XR-Naltrexone is FDA approved for the treatment of alcohol use disorders and has an excellent established safety profile. The serious adverse drug event rates are low and the drug is generally well tolerated. Based on available evidence, it is the most effective pharmacotherapy for alcohol use disorders. The benefits to participants of receiving a safe, established, effective treatment for their alcohol use disorder include reduction in total alcohol consumed, reduction in heavy drinking days, and increased success with achieving sobriety if desired. Based on current research literature, reduced days of heavy drinking and total alcohol use can be reasonably expected to lower the risk of alcohol related disease and alcohol related trauma. These are associated with significant cost, both personal and financial, to both patients and society.

IV. Analysis, Measurements, and Outcomes:

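### No eligibility criterion or pre-dose check asks about a recent XR-NTX injection, so a patient injected at a community site within the past month would qualify for another 380 mg at the index visit

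*Combined protocol and SAP*

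**What the plan says.** The protocol considers extra doses in one place, Risks and risk minimization strategy in section III. It concludes, "so there is no concern that a patient will receive extra doses during ED visits at locations other than UCSF", because EDs in the city do not give the drug. The next sentence lists a sobering center, a street medicine service and another community organization as places "where XR-Naltrexone is available and is administered to patients", and the text adds: "These community sites are key stakeholders in the treatment of patients with AUD". The same paragraph promises coordination with community organizations and a stakeholder committee that meets quarterly, can hear safety concerns and reviews adverse events.

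The dosing rule is under Enrollment: "Patients meeting all criteria will be enrolled into the study and will receive 380mg of extended-release naltrexone". Visit 2-3 study procedures sets a monthly interval for up to three consecutive months.

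Under Determination of Eligibility, staff look at recent laboratory and toxicology results. "They will also review the past medical history and allergies in the electronic medical record", for the stated purpose of finding cirrhosis or an allergy to the product. They speak to the ED provider "to confirm the patient is willing to be approached, is clinically sober, and medically stable". With an interested patient, the staff member "will confirm the accuracy of information obtained from the medical record review that pertains to inclusion and exclusion criteria".

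**The concern.** The protocol treats extra doses as a risk worth addressing, but its answer covers only other EDs. The sources it names straight afterwards are the ones that could already have treated a patient with alcohol use disorder who then comes to the UCSF ED. If no step asks about this, staff who follow the protocol exactly could give a second depot injection before the first has run its month.

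What is at stake is patient safety at the index dose. Section III lists hepatitis, lowered platelet counts and interference with opioid analgesia as risks of the drug. The documents give no information on doses closer together than monthly. A recorded date would also let the report identify participants who had already been treated elsewhere, which matters when the intervention is described as ED-initiated.

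**Working it through.** The protocol states no figure on this point, so the check is a reading of each step before the index dose. The test case is a patient who received XR-NTX at a community site 14 days earlier and is otherwise eligible.

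1. **Initial Screening.** The shared ED platform is described as holding ED visit dates and diagnoses. Nothing says that it shows community injections.
2. **Chart review (Determination of Eligibility).** It covers liver tests, platelets, pregnancy, opioid toxicology, cirrhosis and allergy. Prior XR-NTX is not on the list.
3. **Talk with the ED provider (same section).** Its stated purpose is willingness, sobriety and stability.
4. **Confirmation with the patient (same section).** It is limited to record information that bears on the criteria. Prior XR-NTX is not a criterion, so it falls outside.
5. **Inclusion and Exclusion Criteria.** Naltrexone appears only as hypersensitivity. The other exclusions are opioid use, liver disease, low platelets, an acute need for opioids, pregnancy and incarceration. The test patient meets none of them.
6. **Enrollment tests.** These cover opiates, platelets, pregnancy and liver disease.
7. **Drug release (Medication storage and distribution).** The stated check is on consent.
8. **Index ED visit.** The Addiction Severity Index supplies a substance use history as baseline data. It is not described as a pre-dose check and is not directed at XR-NTX.
9. **Index visit follow up.** The bracelet or wallet card is issued by the study before the patient leaves the ED, so it cannot flag an earlier community injection.
10. **Risks and risk minimization strategy.** Patients are asked about liver disease and opioid use before the first dose, and about liver symptoms at later ones. Prior XR-NTX is not asked about.

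The test patient passes every step, and the Enrollment rule then gives 380 mg on day 14 of a monthly interval.

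The only timing rules are under Handling of missed injection visits: within 2 weeks, 2-4 weeks, and more than one month. All of them concern late doses. No minimum time since a previous injection is stated anywhere.

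On frequency, the closest figure is in section I: fewer than 1 in 4 dependent patients receive any of the four approved agents. It does not isolate XR-NTX, the past month or this study's population. It suggests that a recent injection is uncommon, but it gives no rate.

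**The case against.** The strongest reply is that a competent prescriber, an ED pharmacist or the patient would bring up a recent injection, and that the consent discussion or the substance use interview might reveal it. That may well happen. But no step requires the question or makes the answer a reason to wait, and the pharmacists are trained on a protocol that does not contain the check. The protocol does write out other questions of this kind, such as opioid use in the past 7 days.

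A second reply is that the team will coordinate with the community organizations and has the quarterly committee. This deserves credit, but it is not a check on an individual patient before a dose, and the sobering center is not named among the committee's members.

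A third reply is that no harm has been shown and that the protocol describes the drug's safety profile as excellent. This stands as a limit on the point: the documents support neither a rate nor a severity.

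Stronger readings are tempting, and the documents do not support them:
- **Double dosing is likely in this trial.** Any probability would rest entirely on an assumed share of recently injected patients.
- **The before-after comparison of ED visits would be distorted.** Nothing allows such an effect to be sized.
- **The dose-count covariate in section IV already captures earlier doses.** The feasibility outcomes in the same section count doses during the study period, and the covariate most naturally means the same.

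After enrolment the gap is narrower, because the case manager coordinates injections, later doses are tracked and participants carry the card or bracelet.

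**Conclusion.** The omission is real, and it lies in the eligibility rule itself: followed as written, that rule allows a second injection inside the protocol's own monthly interval. Confidence is high that the check is absent from the text. It does not extend to how often the event would occur or how much harm it would do. The event is probably uncommon, and no effect on the paired t test is claimed.

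The conclusion rests on the documents as published. The data collection forms and the study order link are not among them and might contain such a question, but the protocol does not call for one. The right label is a cheap improvement for patient safety.

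**What to change.** Add a required screening question before the index dose: the date of the last XR-NTX injection from any source. This will rest mainly on self-report, since nothing indicates that community injections appear in the UCSF record or the shared ED platform. Support it with the chart, or a call to the community provider, where possible.

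If the date falls within the monthly interval, defer enrolment and dosing until the interval has passed. The protocol already accepts deferral when comprehension is in doubt: "the patient will not be enrolled at that time, but may be eligible in the future". Record the date.

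Revise the paragraph in Risks and risk minimization strategy to acknowledge the community sites as a possible source of extra doses and to cite the new check. Ask the same question before later and rescheduled study injections, alongside the liver-symptom questions.

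The cost is one form item and a short amendment. The downside is that a few deferred patients may not return to enrol.
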